Preliminary Data. The pilot data to justify the current trial was a dose-response study that randomized 39 subjects with stage I-III colon cancer to 150 min/wk or 300 min/wk of aerobic exercise or a usual-care control group for 24 weeks.⁴⁸ We identified an interaction between cancer stage (a randomization stratification factor in the pilot study) and randomized group for changes in high-sensitivity [hs]-CRP ($P_{\text{interaction}}=0.051$) and IL-6 ($P_{\text{interaction}}=0.002$). Compared to baseline, 150 min/wk exercise reduced hs-CRP ($-0.79\pm 0.38 \text{ mg/L}$; $P=0.038$) and IL-6 ($-0.57\pm 0.29 \text{ pg/mL}$; $P=0.047$) in subjects with stage III but not in subjects with stage I/II disease. Compared to baseline, 300 min/wk of aerobic exercise did not reduce hs-CRP or IL-6. Additional analyses demonstrated that compared to baseline, 150 min/wk of aerobic exercise reduced fasting plasma insulin ($-28.0\pm 8.4 \text{ pmol/L}$; $P=0.001$) and glucose ($-0.39\pm 0.1 \text{ mmol/L}$; $P=0.011$),⁴⁹ and CTCs ($-1.3\pm 0.3 \text{ cells/mL}$; $P<0.001$).⁵⁰ However, due to the multiple randomized groups of this pilot trial, the sample size within each group was small ($n=12-14$), making between-group comparisons statistically underpowered. The results obtained from this pilot study inform the primary and secondary aims for the proposed trial, as detailed below.

Experimental Design & Methods

A. Number of Subjects

Accrual is 60 subjects (see power and sample size section below), recruited over 24 months, with a monthly accrual goal of approximately 2–3 subjects per month. In our prior trial, we successfully accrued 5.5 subjects per month.¹ Using estimates from our prior trial, we predict we will need to screen approximately 160 potential subjects to successfully randomize 60. We aim to recruit an equal ratio of males and females and ≥25% non-white minority subjects.

B. Inclusion and Exclusion Criteria

Many oncology clinical trials do not reach their minimum projected accrual goal.⁵¹ To ensure trial completion, we implement prospectively specified stepped inclusion and exclusion criteria that enable the efficient recruitment of the most homogeneous study population that is feasible within the allowable time horizon without compromising subject safety or scientific validity.

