- The concentration of high-sensitivity CRP will be determined using an immunoturbidimetric assay (Roche Diagnostics, Indianapolis, IN). This high-sensitivity assay has a limit of detection of 0.03 mg/L. The day-to-day variability of the assay at concentrations of 0.91, 1.60, and 18.40 mg/L are 3.8, 3.3 and 1.9%, respectively.
- IL-6 is measured by an ultra-sensitive quantitative sandwich enzyme immunoassay (R&D Systems, Minneapolis, MN). The assay has a sensitivity of 0.094 pg/mL, and the day-to-day variability of the assay at concentrations of 0.49, 2.78, and 5.65 pg/mL are 9.6, 7.2, and 6.5%, respectively.
- sTNF α -R2 is measured by a quantitative sandwich enzyme immunoassay assay (R&D Systems). The assay has a sensitivity of 0.6 pg/mL. The day-to-day variability of the assay at concentrations of 89.9, 197, and 444 pg/mL are 5.1, 3.5, and 3.6%, respectively. Masked quality-control samples are interspersed among cases, and all lab personnel are blinded to patient outcomes.

Insulin Resistance. An assessment of insulin resistance will be performed using a 75-gram oral glucose tolerance test. Plasma glucose and insulin concentrations will be determined at pre-specified intervals to calculate the incremental area under the curve during the oral glucose tolerance test.

Circulating Tumor Cells (CTCs). CTCs from participant venous blood will be isolated using a geometrically enhanced differential immunocapture (GEDI) platform. GEDI is a microfluidic platform that utilizes antibody-coated obstacles to capture rare cells within the blood. This allows for anticoagulated whole blood to be applied to the “chip” the size of a microscope slide in the laboratory using standard syringe pumps. To capture CTCs, obstacles will be coated with an antibody specific to epithelial cell-adhesion molecule (EpCAM), an epithelial cell-specific marker. After washes, captured cells will be stained with the nuclear marker DAPI and fluorescently labeled antibodies to the leukocyte marker CD45 and the epithelial cell marker Pdx-1. Using fluorescence microscopy, Pdx1+/DAPI+/CD45- EpCAM captured cells with intact cellular morphology will be counted as CTCs by a blinded technician. Cells will be stored at -80°C for additional analyses in subsequent grant submissions.

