The primary hypothesis in this trial is that exercise will significantly lower plasma inflammation concentrations over 12 weeks compared to control. All inferential analyses will be conducted on an intention-to-treat basis. Plasma inflammatory concentrations will be log-transformed in the inferential analysis to improve normality. Changes in outcomes will be evaluated from baseline to follow-up in the two groups using a repeated-measures mixed-effects regression model that accounts for the correlation between repeated measures and is robust to missing data. The baseline value of the dependent variable and sex (randomization stratification factor) will be included as a covariate in the regression models.⁵⁵ Group-by-time interaction terms will be included as fixed effects in the regression model. Model fit will be assessed using standard methods. A closed testing procedure for the two study outcomes (hs-CRP and IL-6) will be used, which is hierarchically ordered to test CRP and then IL-6 to maintain the overall experiment-wise error rate at 5%.⁵⁶ Other inflammatory outcomes and measures of insulin resistance (Aim 2) and CTCs (Aim 3) will be analyzed using the same statistical techniques and reported at the nominal type I error rate of 5%.

Data and Specimen Management

Study participants will be assigned unique subject identification (ID) numbers. Study subject ID numbers will be used on all data collection instruments, including questionnaires, data collection forms, biological specimen tubes, and computer records. A master list linking the participants' names and ID numbers will be kept in a password-protected computer file with access restricted to the PI and co-PIs. Biological samples that are moved off-site for analysis will not contain any personally identifiable information and will be labeled with only the unique subject ID numbers. Staff at these sites will not have access to the master list at any time.

Data collection forms will be kept under lock and key or password-protected if computerized and under the control of the PI, co-PIs, and medical investigator. Only personnel assigned to the research study by the PI will have access to the data. Hard-copy data records will be stored for a minimum of three years after study completion.

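### Do circulating tumor cell counts need their own count model and zero rule in the analysis plan?

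*Combined protocol and SAP*

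**What the plan says.** Under Procedure Descriptions, the CTC measurement is a cell count in whole blood: "This allows for anticoagulated whole blood to be applied" to the capture chip, and "captured cells with intact cellular morphology will be counted as CTCs by a blinded technician". The volume of blood processed is not stated. Preliminary Data reports the pilot effect on the raw scale, a fall of 1.3 ± 0.3 cells/mL.

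The Statistical Analysis section describes a repeated-measures mixed model for the inflammatory markers. Four of its sentences matter here:

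- Scale: "Plasma inflammatory concentrations will be log-transformed in the inferential analysis to improve normality".
- Covariates: "The baseline value of the dependent variable and sex (randomization stratification factor) will be included as a covariate".
- Analysis set: "All inferential analyses will be conducted on an intention-to-treat basis".
- Checking: "Model fit will be assessed using standard methods".

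It then extends the approach: "Other inflammatory outcomes and measures of insulin resistance (Aim 2) and CTCs (Aim 3) will be analyzed using the same statistical techniques", at a nominal 5%. No section names a CTC scale, an error distribution, a treatment of zeros or an alternative model.

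**The concern.** CTCs are one of two secondary objectives, and a count can be zero at either visit. The Background cites a cohort in which 31% of patients had tumor cells after treatment, so 69% had none. If the same techniques include the log transform, a zero is undefined both as outcome and as baseline covariate. The analyst would then have to drop zeros, which excludes randomized participants because of their result, or add a constant, whose size moves the estimate.

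If the scale could be chosen after the counts were seen, the estimate and its P value could depend on that choice. A negative binomial model named in advance would appear to settle the matter cheaply.

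**Working it through.** **1. What the text prescribes.** The log sentence names a class of variables, plasma inflammatory concentrations. CTCs are not in that class: they are whole-blood counts, and the pilot reported them in cells/mL. The shared techniques are therefore the baseline-adjusted mixed model, without the log. On the raw scale a zero is an ordinary value on both sides of the model. Nobody is dropped and no constant is needed. With one follow-up visit, the group contrast is taken to be a regression of the month-3 count on group, baseline count and sex.

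**2. Is that reading valid?** Simulation inputs:

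- From the plan: 30 per arm, randomized within sex.
- Assumed: zero share 20, 40 or 69%; baseline gamma shape k of 0.3, 0.5, 1 or 2; visit-to-visit variation none, moderate or large.
- Size: 36 settings, 2,000 trials per run.

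With no effect, the raw model rejected in 3.0–5.8% of trials.

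**3. Where the distortions come from.** With 20% zeros, shape 2, stable counts and a true ratio of 0.40, the median estimates were:

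| Analysis | Estimated ratio |
|---|---|
| Log, 0.01 added | 0.20 |
| Log, zeros dropped | 0.59 |
| Log, 1 added | 0.61 |
| Negative binomial | 0.40 |

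The first three are log variants that the plan does not state. Dropping zeros also conflicts with its intention-to-treat sentence.

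**4. Would a count model gain power?** Power of the re-randomized negative binomial test minus raw power, in percentage points:

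| Baseline shape | True ratio 0.40 | True ratio 0.60 |
|---|---|---|
| 1–2 | −2 to +8 | −4 to +4 |
| 0.5 | −3 to +19 | −5 to +14 |
| 0.3 | −3 to +32 | −11 to +24 |

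The large gains need strong skewness. Two checks against the plan's own figures make that unlikely.

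*Blood volume.* The mean count for zero share p0 is m = k(p0^(−1/k) − 1). At k = 0.3 and p0 = 0.20, m = 0.3 × (0.20^(−3.33) − 1) = 63.8 cells. A fall of 1.3 cells/mL at ratio 0.40 then needs 0.60 × 63.8 / 1.3 = 29.5 mL of the 70 mL draw. Every gap above 20 points lies at this mean count.

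*Pilot precision.* For hs-CRP in the same paragraph, 0.79/0.38 = 2.08, which agrees with its P of 0.038, so ± is a standard error. For CTCs, with 12–14 per group, the SD of change is 0.3 × √12 = 1.04 to 0.3 × √14 = 1.12. Under a gamma model with a proportional effect, the SD of change is at least 1.3/√k. So k must be at least (1.3/1.12)² ≈ 1.35. A shape of 0.5 would need (1.3/√0.5/0.3)² ≈ 38 participants to reach that standard error. A shape of 0.3 would need about 63, more than the 39 in the whole pilot.

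*Pilot-compatible settings.* With stable counts, shape 1.35–2 and an assumed 1.1–5 mL processed (400 trials each), raw was equal or better in all nine settings. Three of them:

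| Setting | Raw | Count test | Log(x+1) |
|---|---|---|---|
| Shape 2, 1.1 mL, ratio 0.60 | 54% | 54% | 50% |
| Shape 2, 5 mL, ratio 0.70 | 84% | 82% | 71% |
| Shape 1.35, 5 mL, ratio 0.70 | 84% | 78% | 64% |

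*A separate simulation*, raw versus count test: 61/60, 87/82 and 79/78% with stable counts; 29/30, 40/41, 24/29 and 59/63% with visit-to-visit variation. The differences run from −5 to +5 points. In one skewed setting log(x+1) beat the count test, 74 to 63%.

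**5. The plan's only CTC design figure.** The Power analysis section calls 60 participants adequate for d ≥ 0.3. With 30 per arm, d√(n/2) = 0.3 × √15 = 1.16, and 1.16 − 1.96 = −0.80 gives 21% power two-sided. That claim does not reproduce, but it is a separate matter that the choice of CTC model does not repair.

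**The case for a change.** The strongest case rests on pre-specification. The scale is nowhere written down. With no effect, each of six analyses (raw, four added constants, zeros dropped) rejected in about 4–6% of trials, but the most favorable of the six rejected in 12–15%. A second simulation gave 10–13%. The proposed count analysis recovers a true ratio of 0.40 as 0.38–0.41, and its re-randomization test held size at 3.8–5.9%.

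It stands that the text leaves the scale to be inferred, and that searching across analyses would inflate error. But five of the six analyses are log variants outside the natural reading, so the inflation measures a departure from the plan.

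The accuracy of the count model is partly built in, because the data were generated from the distribution it assumes. Nor is it simple. The ordinary likelihood-ratio test rejected in 9–12% of null trials at 69% zeros, and the Wald interval fell below 93% coverage in 63 of 108 runs. It therefore needs re-randomization, test inversion and a recorded blood volume for an assay run off-site.

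Two limits apply to the defense of the raw model. The pilot bound on skewness treats the reported standard error as specific to one arm; a pooled error would loosen it. And where counts vary between visits, the count test can be somewhat more powerful.

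**Conclusion.** No change is needed. The missing scale is a detail that a competent analyst fills from the text: raw counts, baseline-adjusted, zeros kept. That analysis is valid at this sample size (type I error 3.0–5.8%) and consistent with the intention-to-treat sentence. Saying so explicitly would be harmless tidying, but the soundness of the result does not depend on it.

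Replacing the linear model with a count model is a trade-off on which statisticians may reasonably differ. Its power is within 5 points of raw in the separate checks, and in the wider grid it is up to 11 points lower at ratio 0.60. The larger gains require skewness that sits badly with the pilot's standard error.

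These conclusions rest on assumed zero shares, dispersion and effect ratios; the 69% zero share comes from another cohort. No sex effect or missing data were simulated in the main grid. The co-primary hs-CRP and IL-6 tests are not touched.
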